### 3.3. Data collection

For all consecutive eligible patients included in the study from each participating Institution, their medical records will be retrieved and anonymized data entered into a database. The following information will be collected, if available:

- 1) Baseline characteristics: body mass index; smoking habit; age at menarche; age at menopause; menopausal status at the time of breast cancer diagnosis; use of birth control pills; prior children before breast cancer diagnosis; history of spontaneous abortion; history of induced abortion; prior treatment for infertility; prior gynecological surgery and/or medical history with possible impact on fertility.
- 2) Breast cancer history: date of diagnosis; age at diagnosis; disease stage; laterality of the primary tumor; type of breast and axillary surgery; use of breast reconstruction surgery; grade; histology; tumor size and nodal status (for patients who underwent primary systemic therapy, only clinical tumor size and nodal status will be collected); hormone receptor status (estrogen and progesterone receptors); HER2 status.
- 3) Treatment of the primary tumor: timing of systemic therapy administration; use of chemotherapy (type and number of cycles); use of endocrine therapy (type and duration); use of anti-HER2 targeted therapy (type and duration); use of radiotherapy.
- 4) Survival status: any recurrence of invasive breast cancer including date of the event; any second primary breast cancer including date of the event; any second primary malignancy including date of the event; date of last follow-up and/or death; cause of death (breast cancer-related or not).
- 5) Ovarian function after chemotherapy: treatment-induced POF; age at menopause.

6) Pregnancy after breast cancer: any pregnancy including date of the event; pregnancy outcome; gestational age at delivery; any pregnancy/fetal/birth complications; breastfeeding and its duration; use and type of ART.

7) BRCA mutation: date of *BRCA* testing; type of *BRCA* mutation; use and date of breast prophylactic surgery; use and date of gynecological prophylactic surgery.

8) Additional information: diagnosis of breast cancer during pregnancy, availability of digital scanned images for TILs analysis

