To evaluate the safety of ART procedures following breast cancer diagnosis in *BRCA* mutated survivors, two groups of patients within the pregnant cohort will be considered: patients who achieved pregnancy with the use of any ART procedure (i.e. “ART group”) and patients who achieved pregnancy without the use of any ART procedure (i.e. “no ART group”). A subgroup analysis will be performed to evaluate the safety of controlled ovarian stimulation as part of ART within the ART group.

In patients who underwent chemotherapy as part of (neo)adjuvant systemic therapy, the impact of anticancer therapies (i.e. chemotherapy) on patients’ ovarian function, in terms of incidence of treatment-induced POF and age at menopause will be evaluated, if available. According to the World Health Organization definition of postmenopausal status [23], treatment-induced amenorrhea will be defined by the absence of menses for  $\geq$  12 months after the end of chemotherapy. Age at menopause will be defined as age in which patients had absence of menses for  $\geq$  12 months. For patients who

developed treatment-induced amenorrhea but then had a recovery of menses more than 12 months after the end of chemotherapy and with active menstrual function within 12 months prior to the last follow-up visit, they will not be considered as having developed menopause. Subgroup analyses will be performed according to age at diagnosis, type of chemotherapy used (anthracycline- and taxane-based regimens vs. anthracycline-based regimens vs. other regimens), and use of endocrine therapy (yes vs. no). These results will be compared to historical data in the *BRCA* wild-type breast cancer population.

Considering the sample size and the uniqueness of the young cohort of *BRCA* mutated patients expected to be included in the study, additional analyses will be conducted to describe baseline, tumor and treatment characteristics as well as patterns of care including access to risk-reducing surgeries. Possible changes over time will be also assessed. Moreover, similarly, the prognostic impact of baseline, tumor and treatment characteristics as well as of risk-reducing surgeries in *BRCA* mutated patients will be also evaluated.

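### The recovery rule for treatment-induced amenorrhea depends on menstrual status at the last visit, so later loss of menses from other causes can be counted as a chemotherapy effect and dated to the post-chemotherapy episode

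*Combined protocol and SAP*

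**What the plan says.** Section 4 evaluates the effect of chemotherapy on ovarian function "in terms of incidence of treatment-induced POF and age at menopause will be evaluated, if available". It gives three rules.

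- **Amenorrhea:** "treatment-induced amenorrhea will be defined by the absence of menses for" at least 12 months after chemotherapy ends.
- **Age at menopause:** "Age at menopause will be defined as age in which patients had absence of menses for" at least 12 months. The text does not say which episode counts if there are two, and makes no exception for lactation, surgery or drug-induced amenorrhea.
- **Recovery:** this covers women who "developed treatment-induced amenorrhea but then had a recovery of menses more than 12 months after the end of chemotherapy" and adds a second condition, "with active menstrual function within 12 months prior to the last follow-up visit, they will not be considered as having developed menopause".

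POF is named as an endpoint, but section 4 defines only amenorrhea and menopause, and the recovery rule speaks of menopause.

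Section 3.3 lists the ovarian data as "Ovarian function after chemotherapy: treatment-induced POF; age at menopause". It lists no date of menses return or of last menses. It does list pregnancy dates, breastfeeding duration, use and type of ART, type and duration of endocrine therapy, and the date of prophylactic gynecological surgery.

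**The concern.** The analysis is meant to measure what chemotherapy did to the ovaries. Whether a woman menstruated in the year before her last contact also reflects her age by then, any surgery, her current drugs and whether she is breastfeeding. A woman whose ovaries demonstrably recovered can fail the exception for any of these reasons.

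Two results are at stake: the incidence of treatment-induced POF, which could be too high, and age at menopause, which could be too low. Both feed further comparisons. The plan states that "Subgroup analyses will be performed according to age at diagnosis, type of chemotherapy used" and by use of endocrine therapy, and that results will be set against historical data from women without a BRCA mutation. A definition that drifts with follow-up makes those comparisons harder to read.

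**Working it through.** The documents give no POF rate, sample size or power for this analysis, so there is no figure to reproduce. The check applies the rule to individual histories.

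**Step 1: which condition decides.** A woman reaches the recovery rule only after at least 12 months without menses following chemotherapy. Any return of menses therefore comes at or after 12 months, and the timing condition adds almost nothing to recovery itself. The last-visit condition does the work.

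**Step 2: what happens if it fails.** The rule says who is not menopausal. It does not say how to class a recovered woman who fails the second condition. It is the only exception given, so the general definition is what remains, and her post-chemotherapy episode already meets that definition.

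**Step 3: pregnancy and lactation.** Assumptions from outside the documents: gestation of 37 to 42 weeks counted from last menses, and 30.4375 days per month.

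Months since last menses at delivery = weeks × 7 / 30.4375. Post-partum amenorrhea needed to pass 12 months = 12 minus that value.

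| Gestation | Months since last menses at delivery | Further months needed to fail |
|---|---|---|
| 37 weeks | 8.51 | 3.49 |
| 40 weeks | 9.20 | 2.80 |
| 42 weeks | 9.66 | 2.34 |

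A recovered woman who is pregnant at her last visit is inside the window and meets the rule, unless she conceived without menses in the preceding months. After a 40-week pregnancy, a breastfeeding woman without menses is at 9.20 + 2 = 11.2 months two months post partum (meets the rule), 12.2 at three months (fails) and 15.2 at six months (fails).

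**Step 4: other causes.** If menses stopped 24 months before the last visit, then 24 > 12 and the rule fails, whether the cause was natural menopause, surgery or ovarian suppression. Surgery is a realistic route: section 1 reports that removal of the ovaries and tubes is generally advised for carriers at 35 to 40 once childbearing is complete, and every patient is a carrier diagnosed at 40 or younger.

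**Step 5: a worked history (hypothetical).** A woman is diagnosed at 38 in 2002, has 15 months of amenorrhea after chemotherapy, then about ten years of menses, reaches natural menopause at 50 and is last seen in 2022 at 38 + 20 = 58. Her menses stopped about 58 − 50 = 8 years before that visit, so she fails the exception. Her first 12-month absence was complete at about 39. Dating menopause to that episode instead of 50 moves it by about 11 years.

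**Step 6: dependence on follow-up.** Diagnoses run from 2000 to 2020. A woman aged 40 at diagnosis in 2000 would be 40 + 22 = 62 in 2022, the year of the current protocol version, and 70 in 2030, the stated end of the study. One aged 40 at diagnosis in 2020 would be 42 and 50. Early diagnoses leave far more time for menses to stop for other reasons.

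**The case against.** The strongest reply is that the plan never says recovered women stay menopausal. That is right as to the wording: the result is inferred from the absence of any other rule. Even on the kinder reading, the plan leaves open how these women are counted for POF and which episode sets the age.

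A second reply is that a woman who recovered and later reached natural menopause is menopausal. This also stands. Her status is correct; what can be wrong is the attribution to chemotherapy and the age recorded.

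A third reply is that recent menses is a sensible test of sustained recovery, since one isolated bleed proves little. This has merit, but sustained recovery can be judged from the period after chemotherapy without using the last visit.

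Stronger readings are tempting and not supported:

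- A reader might infer that women pregnant at last visit are misclassified. Pregnancy alone stays within 12 months.
- A reader might infer that the regimen comparison is confounded by follow-up. That requires regimen use to have shifted over the accrual period, which the documents do not say.
- A reader might try to size the error by simulation. The age distribution, loss to follow-up and age at natural menopause would all come from outside the documents. The rule also reaches only women with at least 12 months of amenorrhea followed by recovery, so a share taken over all women without permanent ovarian failure would use the wrong denominator.

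**Conclusion.** The concern holds in this form: applied as written, the rule can count a recovered woman's later loss of menses as a chemotherapy effect and date it to the post-chemotherapy episode. The causes are natural menopause, prophylactic gynecological surgery, ovarian suppression, and lactational amenorrhea beyond about 2.3 to 3.5 months post partum.

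The direction is towards a higher POF incidence and a lower age at menopause, with more scope for error the longer the follow-up. The size cannot be calculated from the documents. The conclusion rests on treating the single exception as the only way out of the general definition, and the lactation threshold rests on the assumed gestation.

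The change is worth making but limited in reach: this is a secondary analysis, done only where data exist, and the survival endpoints and pregnancy rate are untouched.

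**What to change.** In the ovarian-function paragraph of section 4:

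1. Remove the last-visit condition from the classification of treatment-induced POF, and define POF explicitly in relation to amenorrhea and menopause.
2. Class a woman with documented resumption of menses, or a later pregnancy without ART, as not having treatment-induced POF. Say what counts as documentation, so that a single bleed is handled consistently. Pregnancy with ART should not count by itself, because stored or donated oocytes may have been used.
3. Record later natural or surgical menopause as a separate event at its own age, using the surgery date already collected.
4. Do not count lactational or drug-induced amenorrhea as menopause. Pregnancy dates, breastfeeding duration and endocrine therapy details help to identify it.
5. Report POF at a fixed time after chemotherapy only where the date of menses return can be obtained.

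Most of this uses items already listed in section 3.3. The costs are a wording change, some site queries for the date of menses return, and a lower reported POF incidence.

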Concerns about fertility preservation and future chance of achieving a pregnancy are prevalent issues affecting young breast cancer patients [8]. Hence, accordingly, major international guidelines recommend physicians to address with patients as part of informed consent before anticancer therapies the possibility of developing POF and infertility, and then to discuss fertility preservation options in interested patients [9–11]. Specific issues on this regard should be considered in patients with *BRCA* mutation in the context of their unique concerns [12]. For carriers, given the increasing risk of ovarian cancer with age, bilateral salpingo-oophorectomy is generally recommended for both *BRCA1* and *BRCA2* carriers between the ages of 35 and 40 years and upon completion of childbearing [13]. Moreover, some carriers wish to eliminate the mutation from future offspring through pre-implantation genetic diagnosis [14]. Finally, given the increasing risk of ovarian and breast cancer and the risk of developing long-term treatment-related POF [15], the window for fertility and pregnancy may be narrow in such young women. Of note, although, the last years have brought many safety and efficacy data on the available options for fertility preservation increasing the chances of

future offspring in cancer survivors, numerous challenges remain for young breast cancer patients considering fertility preservation and to have a pregnancy after the end of treatments, especially for those with *BRCA* mutations. Thus, further research is needed in the field; particularly, reproduction studies to address the specific issues of women with *BRCA* mutations are lacking and should be considered a research priority.

Approximately 40% to 50% of women in whom breast cancer is diagnosed during childbearing age wish to have a subsequent pregnancy [16]. However, the percentage of breast cancer patients reported in the literature that has at least one full-term pregnancy after breast cancer diagnosis is very low. Of note, among cancer survivors, breast cancer patients have the lowest pregnancy rate with an overall 67% reduction in the chance of giving birth after cancer treatment as compared to the general population [17]. This observation reflects not only the damage to ovarian reserve due to the gonadotoxic treatments required, but also patient and provider concerns related to a possible negative impact of pregnancy on the evolution of breast cancer [18].

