pregnant cohort will be compared to those of patients in the non-pregnant cohort. To reduce the impact of selection bias (i.e. guaranteed time bias), two analyses will be performed. In the extended Cox model analysis with occurrence of pregnancy as a time-varying covariate, all eligible patients included in the study will be considered. In the “case-control” analysis, each patient in the pregnant cohort (case) will be matched with 3 patients from the non-pregnant cohort (controls). To adjust for guaranteed time bias, each patient in the non-pregnant cohort should have a disease-free interval equal to or longer than the time elapsing between breast cancer diagnosis and date of pregnancy of the matched patient in the pregnant cohort. Patients who became pregnant after the date of the DFS event will be dropped from this analysis. Patients will be also matched according to several variables including type of *BRCA* mutation (*BRCA1* vs. *BRCA2*), hormone receptor status (positive vs. negative), nodal status (negative vs. positive), and year at diagnosis ( $\pm 2.5$  years). Because all included patients are aged  $\leq 40$  years at the time of diagnosis, matching according to age will not be performed. The matching will be done centrally at the coordinating center. Two data sets will be constituted: one for the cases and one for the potential controls. Cases will be sorted randomly and matching will be done starting for the first case until the last one. For each case, all possible controls will be extracted from the data set of potential controls. If they are only 2 controls available, matching criteria will be relaxed one by one (starting from year of diagnosis, etc) until at least a third control is found. It is anticipated, given the expected low rate of cases in the full database, to reach matching for almost each case. In these analyses, all survival endpoints will be calculated from the date of pregnancy until the date of the event. In the non-pregnant cohort, survival endpoints will be calculated from the date of diagnosis, adding the time elapsing between diagnosis and pregnancy of the matched pregnant case.

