The prognostic impact (in terms of DFS, BCSS and OS) of pregnancy following breast cancer diagnosis will be then evaluated in various subgroups of *BRCA* mutated survivors according to: type of *BRCA* mutation (*BRCA1* vs. *BRCA2*), hormone receptor status (positive vs. negative), HER2 status (positive vs. negative), exposure to chemotherapy (prior exposure vs. no prior exposure), exposure to endocrine therapy (prior exposure vs. no prior exposure), interval between diagnosis and pregnancy ( $\leq 2$  years vs.  $> 2$  years after diagnosis), outcome of pregnancy (abortion vs. completed pregnancy), and breastfeeding status (breastfeeding vs. no breastfeeding).

Considering a rate of pregnancy of approximately 10%, with 2000 non-pregnant and 200 pregnant *BRCA* mutated breast cancer patients, assuming a DFS rate of 65% at 5 years in the non-pregnant cohort [21], the study will have a power of 0.83 to detect a hazard ratio of 0.75 and a power of 0.62

to detect a hazard ratio of 0.80 in favor of the pregnant cohort, at a two-sided significance level 0.05 (accrual duration 2000-2020, total study duration 2000-2030).

The rate of pregnancy following breast cancer diagnosis will be computed according to the Kaplan-Meier method. A possible increasing or decreasing trend in rate of pregnancy following breast cancer over the years will be also assessed.

The statistical analysis to evaluate the pregnancy, fetal and obstetrical outcomes of the pregnancies following breast cancer diagnosis in *BRCA* mutated survivors will be mainly descriptive and will include the following parameters:

1. Gestational age at delivery;
2. Incidence of early pre-term (< 34 weeks), late-preterm (34-36 weeks) and full-term ( $\geq$  37 weeks) pregnancies;
3. Number of pregnancies resulting in live birth and number of children born;
4. Incidence of induced and spontaneous abortion;
5. Incidence and nature of pregnancy complications (if any);
6. Incidence and nature of fetal complication and/or congenital malformations (if any);
7. Incidence and nature of obstetrical complications (if any).

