In order to conduct the evaluation of TILs in this cohort, there will be no need for new cutting/preparation of tumor slides. The evaluation will be conducted on one archived diagnostic tumor-containing slide stained with hematoxylin and eosin representative of the primary tumor. The TILs scoring will be performed centrally. If available, anonymized digitally scanned images of the diagnostic hematoxylin and eosin-stained slide should be sent via email to [name] ([[contact]](mailto:[contact])) at University of Padova-Istituto Oncologico Veneto (Padova, Italy). The University of Padova-Istituto Oncologico Veneto will take care of costs related to TILs scoring and storage support (hard disk). The evaluation will be performed according to the TILs working group recommendations [24].

Patients demographic, clinical and pathologic baseline characteristics will be compared by pregnancy status using chi-square test or Fisher Exact test for categorical variables and Wilcoxon rank-sum test or t-test for continuous variables, as appropriate.

Dichotomous outcomes will be compared using univariate and multivariate logistic regression models. Time-to-event outcomes will be estimated and plotted using Kaplan-Meier methods. Survival rates will be compared using log-rank test and Cox proportional hazards models for univariate and multivariate analysis, respectively.

All tests will be two-sided and p-values of  $< 0.05$  will be considered statistically significant. All

analyses will be performed using standard available statistical programs.

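### Risk-reducing surgery has no stated exposure timing: analysed by the plan's general log-rank and Cox methods from diagnosis, surgery done after diagnosis would look protective with no true effect

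*Combined protocol and SAP*

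**What the plan says.** Section 2 lists the prognostic impact of risk-reducing surgeries as a secondary objective. Section 4 repeats it among the additional analyses, in one phrase with factors known at diagnosis: "the prognostic impact of baseline, tumor and treatment characteristics as well as of risk-reducing surgeries". Neither place names an endpoint, model, time origin or definition of exposure for surgery.

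The only general method for time-to-event outcomes comes at the end of Section 4: "Survival rates will be compared using log-rank test and Cox proportional hazards models for univariate and multivariate analysis, respectively".

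For pregnancy the plan is more careful. It names the problem, "To reduce the impact of selection bias (i.e. guaranteed time bias), two analyses will be performed", and specifies an "extended Cox model analysis with occurrence of pregnancy as a time-varying covariate" together with a matched analysis on disease-free interval. Both are written for pregnancy only, in the Synopsis and in Section 4.

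Section 3.3 collects "use and date of breast prophylactic surgery; use and date of gynecological prophylactic surgery". Section 1 says that salpingo-oophorectomy is generally recommended "between the ages of 35 and 40 years and upon completion of childbearing".

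**The concern.** A woman can be counted as operated only if she reaches the operation. If operated and non-operated women are compared from diagnosis, the event-free time before surgery is credited to surgery, while women who relapse or die first go into the non-operated group. This is the same guaranteed-time bias that the plan controls for pregnancy.

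An ordinary log-rank test compares groups fixed at the time origin, and a Cox model does the same unless a covariate is declared time-varying. An analyst who follows Section 4 literally could therefore treat surgery as if it were known at diagnosis. A named secondary objective could then report a protective association that the analysis itself created.

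**Working it through.** **Is there a figure to reproduce?** The plan gives none for surgery. Its only computed figures are the powers for the pregnancy comparison (0.83 at a hazard ratio of 0.75, 0.62 at 0.80). They play no part in the check below, except that those hazard ratios serve as a scale.

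**Inputs from Section 4.**
- Event rate: "assuming a DFS rate of 65% at 5 years in the non-pregnant cohort". With exponential times, the hazard is λ = -ln(0.65)/5 = 0.0862 per year.
- Size: "with 2000 non-pregnant and 200 pregnant", so 2000 + 200 = 2200 women.
- Accrual 2000-2020 and total duration to 2030, so potential follow-up is 10 to 30 years.

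**Assumptions, because the documents give neither figure.** Uptake is the share who would have surgery if they stayed event-free, set at 30-70%. The delay from diagnosis runs from within 6 months (uniform) to a median of 5 years (exponential). Surgery has no effect on DFS.

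**Hand calculation without censoring.** Take uptake p = 0.5 and a median delay of 2 years, so the surgery rate is μ = ln(2)/2 = 0.3466 per year and λ + μ = 0.4327.
- Operated women: mean time from diagnosis to event = 1/λ + 1/(λ+μ) = 11.61 + 2.31 = 13.92 years. Event rate = 1/13.92 = 0.0719.
- Non-operated women, per woman in the cohort: events = (1-p) + pλ/(λ+μ) = 0.5 + 0.5 × 0.1991 = 0.5996. Person-years = 0.5 × 11.61 + 0.0996 × 2.31 = 6.03. Event rate = 0.0994.
- Rate ratio = 0.0719/0.0994 = 0.72, although the true ratio is 1.

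Now move the time before surgery to the unexposed side. Time after surgery has rate λ. The remaining time has events (1-p) + pλ/(λ+μ) over person-years (1-p)/λ + p/(λ+μ), which is again exactly λ. The ratio is 1.00.

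**Simulation with follow-up of 10-30 years.** 2200 women, 200 replicates, no true effect. Surgery counts only if it precedes the DFS event or censoring. Cox model with ever/never surgery from diagnosis:

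| Assumed timing after diagnosis | Apparent DFS hazard ratio, uptake 30% to 70% | Runs with falsely significant protection |
|---|---|---|
| Within 6 months | 0.96 to 0.92 | 10-41% |
| Within 12 months | 0.93 to 0.85 | 30-90% |
| Median 1 year | 0.84 to 0.69 | 95-100% |
| Median 2 years | 0.73 to 0.56 | 100% |
| Median 3 years | 0.67 to 0.50 | 100% |
| Median 5 years | 0.60 to 0.46 | 100% |
| Half at primary surgery, half at a median of 3 years | 0.81 to 0.67 | 98-100% |

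A second set of runs gave 0.83 to 0.68 at 1 year and 0.74 to 0.56 at 2 years, so simulation error is about 0.01.

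With surgery as a time-varying covariate, the hazard ratio is 1.00-1.01 in every scenario and two-sided rejection is about 5% (2-9% across scenarios).

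**Sensitivity.**
- If surgery after the DFS event also counts as exposure (death on average 3 years after the event, assumed), the hazard ratio is 0.98-0.96 at a median delay of 0.5 years, 0.87-0.75 at 2 years and 0.74-0.61 at 5 years.
- With a 5-year event-free rate of 80% or 90% instead of 65%, a 2-year median delay gives 0.76-0.59 or 0.78-0.63.

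**The case against.** The strongest reply is that this is silence, not a wrong method. Section 4 never states an ever/never comparison from diagnosis. Its log-rank and Cox sentence is generic and on its face also covers pregnancy, for which an extended Cox model is specified, so it does not exclude time-varying covariates. Collecting surgery dates is compatible with a time-dependent analysis.

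Much of this stands. A reader might infer that the plan prescribes an ever/never analysis, but the documents do not say so. Nor do they require anything else. The sentence on surgery is tied by its linking adverb to the descriptive analyses and changes over time that precede it, not to the pregnancy model. The safeguard is written out for one post-diagnosis exposure and left unstated for another with the same structure.

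A reader might also infer that all surgery follows diagnosis. No section says this. Eligibility does not exclude earlier surgery, prophylactic mastectomy could accompany the primary operation, and the age range in Section 1 is general background on salpingo-oophorectomy. Surgery at or before diagnosis carries no guaranteed time.

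Finally, the objective is secondary and does not touch the primary DFS comparison for pregnancy.

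**Conclusion.** The point holds in conditional form. The plan leaves the timing of surgery undefined, and its general methods permit an analysis that is biased toward protection for whatever share of surgery follows diagnosis. The direction was the same in every scenario run.

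The size depends on uptake, delay and coding, none of which the documents give. The apparent DFS hazard ratio is about 0.92-0.96 if surgery falls within 6 months, 0.68-0.84 at a median delay of 1 year, 0.56-0.73 at 2 years and 0.46-0.60 at 5 years. From a delay of about 2 years, the artefact is as large as or larger than the effects of 0.75-0.80 for which the plan quotes power. It is smaller if surgery after the event also counts, but that coding uses information from after the outcome and is not a remedy.

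A reader might conclude that surgery is bound to look strongly protective, or that the artefact matches any plausible real effect. The first fails for early surgery. The second has no basis, because the documents give no expected effect of surgery.

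**What to change.** Add to Section 4 that, for the surgery objective:
- the time origin is the date of diagnosis, and the endpoint is named;
- risk-reducing mastectomy and salpingo-oophorectomy each enter the Cox model as a separate time-varying covariate, switching on at the recorded date of surgery (or a prespecified landmark analysis is used instead);
- surgery at or before diagnosis counts as exposed from time zero;
- surgery after the endpoint event does not count as exposure;
- Kaplan-Meier curves and log-rank tests by ever/never surgery from diagnosis are not used. Landmark or Simon-Makuch curves would serve for display, but which of them is a matter of preference.

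The cost is a short SAP addition. Surgery dates are already on the collection list, and the start-stop data set is already needed for the pregnancy model.

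The change removes guaranteed-time bias only. Women who choose surgery may differ in prognosis, so the plan should also say that the result remains open to confounding.
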